nurse interventionist. We propose an intervention incorporating 5 individualized, nurse-led, homebased or virtual (phone, HIPAA compliant Zoom or DoxyMe video call) sessions, with telephone check-ins and text reminders, according to participant preference. We have based the timing of study visits on previous experiences of the mentorship team and similar studies with this population, however we will use the open-label pilot interview feedback to provide feedback for further refinement of timing visits. ^{41–43} The intervention will be guided by the theory and evidence-based practices that have been successful

in previous work (Table 1).^{31,41} Every participant will receive each component of the intervention but interventionists will tailor content to each participant's goals.

Nurse interventionists will be trained and equipped with education materials vetted by national organizations leading preventive health research such as the American Heart Association (Healthy for Good⁴⁴) and National Institute of Aging (Go4Life⁴⁵) for each broad category of preventive health behaviors (nutrition, physical activity, stress management, sleep and healthcare utilization).

As part of the intervention, the nurse and caregiver will prioritize the health category that they would most like to address and then set goals. Allowing the caregiver maximum control over this goal setting, without placing additional burden on the caregiver is one aspect of increasing self-efficacy and person-centeredness. Because the intervention will allow participants to pick their own health goals, we will measure goal attainment related to health behaviors, rather than a standardized survey of predetermined preventive health behaviors.

Table 1: Intervention Components and evidence basis for component selection

| Intervention Component | Evidence Basis for Component |
|--|--|
| 1) Whole-person assessment including physical, psychosocial, | - Caregiver physical and psychosocial assessment is suggested by HF guidelines, but not commonly used in practice ^{17,46–48} |
| preventive health behaviors and challenges in caregiving | - Involving the caregiver in assessment and encouraging them to set their own goals is person-centered, builds rapport and increases participation. 41,49,50 |

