| 2) Develop a statement of purpose in life, discussing caregiving in the context of the caregiver's purpose. | Purpose in life was associated with lower mortality and CVD⁵¹, stroke⁵², MI⁵³, better preventive health behaviors⁵⁴, lower allostatic load⁵⁵ Purpose in life can be improved through intervention^{56–58} and is linked to down-regulation of pro-inflammatory genes⁵⁹ |
|--|---|
| 3) Goal setting though co- development of incremental action plans to address personal goals to improve preventive health behaviors and reduce caregiver burden. Caregivers will design and work on incremental action steps related to goals, through tailored strategies aligned with statement of purpose in life. | Incremental action plans based on individually tailored goals, allowing the participant to prioritize their own goals and strategies, increases self-efficacy and encourages participants to use their new skills with other problems. 41,49 Studies incorporating this technique have resulted in improved QOL, self-efficacy related to falls, depression and decreased disability. 41,50,60 Goal attainment achieved in 73% of functionally impaired older adults- independent of age, race, gender – higher pain group less likely to achieve goals. 50 |
| 4) 'Walking meetings' to model the importance of physical activity while discussing progress on incremental action plans to help caregivers achieve goals | Modeling an activity promotes self-efficacy through enactive mastery and vicarious experience^{28,61} Higher social support increases activity levels and motivates caregivers^{13,62-64} Tailored interventions to participants needs increase physical activity.^{13,64} |
| 5) Instrumental support through exploring local resources to access benefits related to medications, healthcare, income assistance, etc. | Instrumental support may enhance emotionally supportive interventions^{65–67} Addressing needs to support instrumental activities of daily living may improve retention from participants Interventions that provide instrumental support while equipping community members are more sustainable and impactful than providing the support without considering social support/network. |

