| day per week | details. 3) RN implements NIA Go4Life physical activities, with emphasis on |
| | variety, strength training and cardio in a safe environment. 3) RN will assess |
| | interest in group activities or engaging social support to increase accountability |
| | and help participant get connected. |
| Stress management: | 1) RN will assess stressors with focus on caregiving-related stress 2) RN will |
| Decrease exposure | work with caregiver to draft a list of caregiving concerns to be addressed at the |
| to stressors, increase | next visit with the patient's cardiologist 3) Participant will identify coping |
| use of coping | strategies such as positive self-talk, ways to defuse stressful situations and |
| strategies | prevent stress through restorative activities focused on purpose in life. |
| Rest: | 1) RN to assess for duration, quality and sleep hygiene 2) RN will help caregiver |
| Improve nighttime | identify modifications to sleep environment and bedtime routine 3) RN will |
| sleep quality | assess for daytime fatigue and sleepiness. |

Table 3: Study Visit Timeline for Immediate Intervention Group*

| Format and | Key activities |
|--------------------------|---|
| timing of visits | |
| Baseline Data Collection | Heartrate Variability Measurement |
| | Survey |
| Randomization | Mail randomization results |
| Virtual Visit | Whole Person Assessment |
| Week 1 | Set goals and discuss priorities |
| | Walking meeting (if virtual: suggest participant take a walk during call) |
| Virtual Visit | Purpose in Life activity |
| Week 3 | Instrumental Support activity: Benefits Check Up |
| | Assess goal attainment and revisit strategies |
| | Walking meeting (if virtual: suggest participant take a walk during call) |
| Phone Check-in | Review/edit purpose statement |
| Week 4 | Assess goal attainment and strategies to achieve goal |
| | Walking meeting (suggest participant take a walk during call) |
| Virtual Visit | Social Support Activity |
| Week 6 | Assess goal attainment and strategies to achieve goal |
| | Follow-up re: instrumental support |
| | Walking meeting (if virtual: suggest participant take a walk during call) |
| Phone Check-in | Review/edit purpose statement |
| Week 8 | Assess goal attainment and strategies to achieve goal |
| | Walking meeting (suggest participant take a walk during call) |
| Virtual Visit | Review of progress, goals and purpose/closure activity |

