| Week 10 | Discuss how caregiver will involve social support in next goals |
| | Walking meeting (if virtual: suggest participant take a walk during call) |
| Phone Check-in | Review/edit purpose statement |
| Week 12 | Assess goal attainment and strategies to achieve goal |
| | Walking meeting (suggest participant take a walk during call) |
| Data Collection Visit | Heartrate Variability Measurement |
| Week 12 | Survey |
| Data Collection Visit | Heartrate Variability Measurement |

Week 24 Survey

Death of the Patient: If the patient/care recipient of the enrolled caregiver/study participant dies during the study, we will send a sympathy card. In that communication, we will ask the caregiver if they would like to participate a modified version of the intervention for bereavement: 1-3 visits (scheduled every other week) with a nurse for bereavement support within two months of the death of the care recipient. Additional instrumental support resources will be suggested such as grief support groups, referral to Roberta's House and bereavement resources for tasks to complete after someone you love dies. If the caregiver chooses to discontinue their participation, we will discontinue study contact and data collection. Data from caregivers whose care recipient dies will be excluded from analysis of primary and secondary outcomes.

Research Variables and Measurement

We chose measures (Table 2) based on previous RCT experience of mentors as well as those that met the following criteria: 1) possess known reliability and validity with ethnically diverse samples; 2) are sensitive to change from an intervention; 3) have clinical relevance; 4) Common Data Elements to connect this work with the broader literature and 5) represent objective as well as subjective indicators of the domains we seek to impact. Finally, we sought to achieve a balance between psychometric quality and practical considerations such as respondent burden. All instruments with the exception of demographics will be measured at baseline, 12 and 24 weeks. Patient characteristics will be obtained from chart review.

^{*} Waitlist control group will begin intervention at week 12.

Table 4: Constructs, Instruments and Reliability

| Theoretical Construct | Instruments and variables | Cronbach's alpha | | | |
|--|--|---------------------|--|--|--|
| | Contextual Factors | | | | |
| | 1)How well does the amount of money you have take care | | | | |

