Education in protection of human research participants: All investigators have completed the Johns Hopkins University School of Medicine Research Compliance course and have been certified to conduct human research. The course consists of the University of Minnesota Web modules on Informed Consent, the consent Process, and After Informed Consent, Johns Hopkins University School of Medicine module on local IRB requirements, and achievement of a passing score on the Johns Hopkins Knowledge Assessment module. According to the policies of the Johns Hopkins University, approval for this research will be obtained from the IRB office for research using human subjects prior to collecting data. Minorities and women are included in this study, and all data will be presented in group format. Participants will be assigned a code number on initial entry and all subsequent questionnaires will be identified only by code number. Information needed for follow-up contact (names and addresses) will be kept separately from all other data.

Procedures for protecting against and minimizing potential risks: The interviewer will notify the Principal Investigator (a nurse) of any concerns for distress related to the study and participants will receive a follow-up telephone call to assure that the mild distress has resolved. In situations where there is initial severe distress or when the distress has not been resolved, we will consult with our Co-Investigator, [name], FNP-BC. Furthermore, if any physical problems emerge during any of the study for either patients or caregivers, immediate medical attention will be sought for the participant. The research assistants will all be nurses and will be trained to call 911 if they have serious concerns of an emergent issue.

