Plan for reporting unanticipated problems or study deviations: There are only minimal risks associated with the trial. It is anticipated that participants will experience more benefits than risks from their participation in the trial.

Table 5: Specific Alerts and Actions Taken

| Alert | Action to be taken |
|--------------------------|--|
| Medical emergency: | If a JHU research staff person encounters this situation over the phone, the |
| • Chest pains | participant is put on hold and the research staff calls 911 immediately. If |
| • Excessive bleeding | situation occurs within home, then staff person calls 911 immediately, and |
| • Fall and cannot get up | stays with participant until help arrives. Research coordinator (RC) and PI |
| Difficulty breathing | are informed within 24 hours of the event. RC then contacts individual as a |
| | follow up within two days. Research staff member completes alert form and |
| | gives to RC (or designate) |
| Evidence of abuse | Evidence of physical abuse is as follows: |
| | Participant states to research staff that abuse occurs. |

| | • Research staff observes physical evidence (e.g., black eye, black and blue marks on arms/legs). |
|--|---|
| | Research staff member informs participant that a senior member of the research team will contact him/her later that day. Staff member informs RC immediately upon completion of interview or intervention session. RC (or designate) contacts participant to obtain further information. Participant is strongly encouraged to call his/her physician and/or Adult Protective Services (phone number will be provided). Based on the situation, the RC may notify Adult Protective Services. RC (or designate) completes Alert form. Note –The possibility of informing an agency about an abusive situation is stated in the informed consent. |
| Extreme Home Hazards | Research staff member notifies RC within 24 hours. RC (or designate) |
| Exposed electrical | completes Alert form. |
| External door missing | |
| or cannot be locked | |
| Ceiling, floors caved | |
| in | |
| • No temperature control (no air or heat; must be extreme) | |
| Major infestation | |

PI – Principal investigator; RC = Research Coordinator

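### Table 5's phone-emergency rule has no step to establish where the participant is, although Table 3 suggests a walk at every remote intervention contact it lists

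*Combined protocol and SAP*

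**What the plan says.** **The walk.** Table 1 in section 4 (Study Procedures) makes walking meetings an intervention component, meant "to model the importance of physical activity while discussing progress on incremental action plans". Under Intervention Delivery Characteristics, "Every participant will receive each component of the intervention", with content tailored to goals. In Table 3 each virtual visit carries the line "Walking meeting (if virtual: suggest participant take a walk during call", and each phone check-in carries "Walking meeting (suggest participant take a walk during call". Besides home visits, the intervention may be delivered in "virtual (phone, HIPAA compliant Zoom or DoxyMe video call) sessions".

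**The emergency rule.** The medical emergency row of Table 5 (section 8, Risks) has two routes. Over the phone, the "participant is put on hold and the research staff calls 911 immediately". In the home, the staff member calls 911 and "stays with participant until help arrives". Both routes then lead to notice to the coordinator and PI within 24 hours, a follow-up contact within two days, and an alert form.

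**Other emergency text.** The paragraph in section 8 on minimizing risks says that "if any physical problems emerge during any of the study for either patients or caregivers, immediate medical attention will be sought for the participant". It adds that the research assistants will be nurses trained to call 911. The Adverse Event (AE) Reporting paragraph describes alerts as emergencies unrelated to taking part in the study, refers to developed procedures for them, points to the chart of alerts (Table 5), and says that alerts need not be reported to the IRB.

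**The concern.** The study itself encourages caregivers aged 50 or older to move about during the calls that Table 5 governs. Several of the emergencies in that row (chest pain, trouble breathing, a fall) could happen on a walk. If the participant is away from home and stops being able to speak, staff who follow the written rule may have no location to give the dispatcher. They will also have put on hold the one channel through which they could learn it or notice a decline. What is at stake is a delay in getting help to that participant. This is separate from whether the participant was screened for physical activity, and no endpoint or estimate depends on it.

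**Working it through.** The plan gives no figure to reproduce here. The check is a count followed by a comparison of texts.

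**1. How often a walk is suggested (Table 3 as listed).**

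| Contact type | Weeks | Listed | With a suggested walk when remote |
|---|---|---|---|
| Virtual visit | 1, 3, 6, 10 | 4 | 4 |
| Phone check-in | 4, 8, 12 | 3 | 3 |
| Data collection | baseline, 12, 24 | 3 | 0 |

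Intervention contacts: 4 + 3 = 7, of which 4 + 3 = 7 carry the suggestion. Data collection: 0 of 3. Table 3 is for the immediate group; its footnote has the waitlist group start the intervention at week 12, and I assume the same contacts for them.

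**2. What the phone rule does, step by step.** Emergency recognized; participant on hold; 911 called; internal notices; alert form. Steps that establish location: 0. Steps that keep live contact: 0. The row names the phone only, although sessions may also be by video.

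**3. Whether another text supplies the location.**
- *Staff training (section 8).* Nurses trained to call 911. This secures the call, not the location.
- *Home address.* The confidentiality text in section 8 describes a master log with name, address and telephone number. A home address does not locate someone out walking.
- *Alert procedures (AE Reporting).* The text points to the chart, and Table 5 has no location step.
- *Contact script.* No section tells staff to ask for location at the start of a remote contact.

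Location steps found outside Table 5: 0.

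**4. Whether Table 5 applies.** AE Reporting limits alerts to emergencies unrelated to study participation. A collapse on a walk that the study suggested is arguably related. So either Table 5 applies and has no location step, or it does not apply and only the general promise of medical attention remains. Neither branch locates the participant. If the event is handled as an alert, it also falls under the statement that alerts need not go to the IRB.

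**5. Size.** Harm requires a remote contact, a walk away from home, an emergency, and inability to speak, all together. The documents give no probability for any of these, so no expected number of events can be derived.

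**The case against.** The strongest reply is that this is operating detail. Nothing forbids staff to ask where the participant is, any 911 call involves giving a location, and being on hold is not the same as being cut off. Intervention contacts are made by nurses. An intervention manual and alert procedures are mentioned but are not in the documents, and a location check may be there. The trial is a pilot of 44 caregivers described as minimal risk.

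Much of this stands, and it limits the point. It does not remove it: a participant who cannot speak cannot answer a question asked only once the emergency has begun, and the written rule has staff leave the live line.

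A reader might also infer several stronger things that the documents do not support:
- *That participants are sent outdoors at every contact.* Each walk is only suggested and may be indoors or near home. Visits may be in person, and phone calls between visits depend on participant preference. The 7 of 7 counts suggestions, not walks or risk.
- *That staff cannot reach the address because the log is locked away.* That text is about confidential storage. Home visits, letters and postcards show that staff use addresses. The problem is only that an address is not a current location.
- *That the in-home rule contradicts the phone rule.* Staff in the home can stay because they are there. The contrast shows no inconsistency.
- *That there is no emergency plan.* There is one, with an immediate 911 call and nurse staff.

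**Conclusion.** The point holds as a gap in a safety procedure that should be closed. All 7 listed intervention contacts carry a suggested walk when remote. The written phone-emergency rule has no location step and suspends live contact, and the stated mitigations do not locate a participant who is walking away from home and cannot speak. The event is likely rare and its rate is unknown, but a single case could be serious, and the walk is the study's own suggestion. Taking the location in advance and keeping the line open is a safer method than the hold rule, so this is more than a missing detail.

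The conclusion assumes that some suggested walks take participants away from home and that no location check sits in the manual. If the manual has one, a reference to it in Table 5 would settle the location part, but the hold instruction would still need changing. There is no effect on outcomes, masking or analysis.

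**What to change.** 1. **Contact script.** At the start of each remote intervention contact, by phone or video, and again when a walk begins, staff confirm aloud the participant's current location or route and a call-back number. They hold these only for the duration of the call. This is done before any audio recording starts or with it paused, because section 8 says recordings will carry no identifying information. The Fidelity text says that ten percent of sessions are audio taped but also that all interactions will be recorded, so the pause may apply to every session. The sponsor should clarify which is meant.
2. **Table 5, medical emergency row.** Replace the phone sentence with: *If staff encounter this situation by phone or video, including during a walk suggested by the study, they call 911 immediately on a second line or by conference call, give the location confirmed at the start of the contact (updated if the participant can speak), and keep the participant on the line until help arrives.* The 911 call stays immediate and does not wait for a location check.
3. **AE Reporting paragraph.** State that the Table 5 medical emergency actions also apply to emergencies during study-suggested walks, and that these events are reported as adverse events. Without this, the new Table 5 wording would conflict with the definition of an alert.

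**Cost.** One script line, one replaced sentence and one added statement; a few seconds per call; a short recording pause; and access to a second line or conference calling. No new data field is needed. A route confirmed when the walk begins can go out of date, so the step reduces the gap rather than removing it.

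### Table 5's abuse steps are worded for a harmed caregiver; if staff see signs of harm on the care recipient, the same steps tell the caregiver of a call before the research coordinator knows, and no time is set for telling the PI

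*Combined protocol and SAP*

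**What the plan says.** The Evidence of abuse row of Table 5 (Section 8, Risks) has two triggers: "Participant states to research staff that abuse occurs" and "Research staff observes physical evidence (e.g., black eye, black and blue marks on arms/legs". The actions follow as running text. The opening one is "Research staff member informs participant that a senior member of the research team will contact him/her later that day". Next, "Staff member informs RC immediately upon completion of interview or intervention session", and then "RC (or designate) contacts participant to obtain further information". The participant is encouraged to call a physician or APS. Finally, "Based on the situation, the RC may notify Adult Protective Services", and the RC or a designate completes the Alert form. A note adds that consent mentions possible notification of an agency.

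The row does not mention the PI. In the medical-emergency row of the same table, the staff member calls 911, "stays with participant until help arrives. Research coordinator (RC) and PI" "are informed within 24 hours of the event".

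Section 4 (Death of the Patient) makes clear that the study participant is the enrolled caregiver and that the heart failure patient is the care recipient.

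**The concern.** Two people may be in the home, and only one of them is the participant. The actions make sense when that person is the one harmed. They work poorly when staff notice injuries on the care recipient, because the caregiver may then be the source of the harm. An announced call could forewarn that person, and the follow-up inquiry is directed to them.

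The situation is foreseeable. Section 5 requires caregivers to share a home with the patient or to visit on three or more days a week. Section 8 (Adverse Event Reporting) recognises that staff may be in the home or see it by video. What is at stake is the safety of a dependent patient, not the trial's estimates.

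**Working it through.** No arithmetic applies; the check is a comparison of texts.

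**1. Whom does the row cover?** The first trigger names who speaks but not who is harmed. The second names the observer and the signs but no injured person. The advice to call a physician or APS is addressed to the participant, which suggests a harmed caregiver was in mind. The row does not say so.

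**2. Where do the steps fit?** Cross the two triggers with the two possible victims:

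| Trigger | Caregiver harmed | Care recipient harmed |
|---|---|---|
| Participant says so | Steps fit | Caregiver raised it, so forewarning does not arise |
| Staff see signs | Steps fit | Caregiver told of a call first, then the only named informant |

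The order is a problem in one of the four cells.

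**3. In that cell, who learns what, and when?** Taking the steps in the order written: (a) the caregiver hears that a senior team member will call that day; (b) the RC is informed when the session ends; (c) the RC or designate contacts the caregiver for more information; (d) the RC may notify APS. The numbering is mine. Step (a) takes place in contact with the caregiver, and step (b) is tied to the end of that contact.

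**4. When does the PI hear?**

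| Event | RC | PI |
|---|---|---|
| Medical emergency (Table 5) | within 24 hours | within 24 hours |
| Evidence of abuse (Table 5) | immediately after the session | not mentioned |
| Extreme home hazards (Table 5) | within 24 hours | not mentioned |
| Serious adverse event (Section 8 text) | not stated | within 48 hours |

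One of the three alert rows gives the PI a time. The 48-hour rule is for serious adverse events, which Section 8 treats separately from alerts. Section 8 also lists alerts among the reports to the PI and gives the PI a supporting role on abuse reporting, but attaches no time to either.

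**5. Is the care recipient covered elsewhere?** The paragraph in Section 8 on minimizing risks provides for medical attention if physical problems emerge in patients or caregivers, and for 911 calls in an emergency. It does not say what to do about suspected abuse. Section 8 refers to developed procedures for alerts, but points to this same chart as the plan for managing and reporting them.

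**The case against.** The strongest reply is that the row is meant for a harmed participant throughout. On that reading Table 5 is silent about abuse of the care recipient; it does not direct staff to alert a suspect. A reader might infer that the protocol instructs staff to warn a suspected abuser. The documents do not support that: the wording points to a harmed caregiver, and the caregiver is told of a call, not of a suspicion. What stands is that the staff-observation trigger carries no such limit. Either the row covers the care recipient and its order is wrong for that case, or it does not and no abuse pathway covers that person.

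Other points reduce the weight of the concern:

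- Consent already mentions possible agency reporting, so the idea is not new to the caregiver.
- The RC's delay is at most the remainder of one session.
- The row does not forbid asking others, and the RC may notify APS without the caregiver's agreement.
- The nurses meet the RC and PI regularly (Section 4, Intervention Protocol and Fidelity). These are routes to the PI, though not a deadline for abuse alerts. It would be wrong to infer that the PI never hears of them.

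A reader might also try to size the exposure by multiplying visits by caregivers. The documents do not support a usable figure. Table 3 labels the four intervention visits as virtual, surveys may be sent by email, and patient data come from chart review or caregiver report, so seeing the patient would be incidental. Any count of scheduled visits would also leave out screening, consent, interviews and the open-label caregivers.

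**Conclusion.** The point holds as a narrow, inexpensive patient-safety improvement. Its size is one trigger-and-victim combination in which the caregiver is told before the RC and is the only named informant, together with no PI time for any abuse alert against 24 hours in the medical-emergency row. The event is expected to be rare, and the documents give no rate and no means of deriving one.

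The conclusion assumes that staff take the steps in the order written and that no fuller staff procedure overrides Table 5; the documents show none. It does not imply that the care recipient is without protection, since medical attention, 911 and APS notification all remain available. Nor does it bear on randomization, outcomes or analysis. The change is worth making, but the trial's validity does not depend on it.

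**What to change.** Amend the abuse row of Table 5 as follows:

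- State that it covers harm to the caregiver or to the care recipient.
- Keep the present steps when the caregiver is the person harmed.
- When the care recipient is or may be harmed, staff inform the RC immediately after leaving or ending the contact, and before telling the caregiver of any call. The RC then decides whom to contact.
- The RC keeps authority to notify APS without waiting for the PI. Requiring a joint decision could delay a report that the RC can now make alone.
- For every abuse alert, inform the PI within 24 hours, matching the medical-emergency row, and record the APS decision on the Alert form.

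The cost is a few lines of text, a short addition to staff training and an occasional prompt notice to the PI. No visits, staff or data are added. The content of the response remains with the responsible clinical and safeguarding leads.
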